## **Background**

The increasing prevalence of multimorbidity, defined as the coexistence of two or more chronic conditions in the same person [1], [2], is driven by the aging population and improved health technologies and represents a major challenge for healthcare systems. In the Capital Region of Denmark and Region Zealand, about 22% and 37% of the citizens aged 16 years and older suffer from multimorbidity [3], [4]. Around 10% of people with multimorbidity have complicated multimorbidity characterized by suffering from a symptom complex with several concomitant chronic conditions [5]. Researchers have proposed different definitions of complicated multimorbidity such as the severity of conditions, perception of illness, and more [6], [7]. Patients with complicated multimorbidity often have reduced health-related quality of life [8], [9], high treatment burden, polypharmacy, reduced ability to work, low employability, and increased mortality [5].

Healthcare systems are designed to take care of patients with single conditions. Unfortunately, the organisation according to specialities causes problems for the provision of integrated care for patients with multimorbidity. Thus, care pathways are often fragmented, with multiple appointments, more frequent hospital admissions, ambulatory visits, and use of other healthcare. The underlying causes for fragmented care are associated with the lack of a clear division of responsibilities and insufficient coordination between healthcare organisations. This is aggravated by non-integrated economic incentives between general practice, municipalities, and hospitals as well as by IT systems that are not always compatible and different care- and leadership cultures. Disease management programs (DMPs) have been developed to support integrated care but these may not be adequate for patients with multiple conditions and lowered self-care ability, and adhering to multiple DMPs may result in too much medication, conflicting treatments, an overload of appointments, and fragmented health care [10]. Also, providing care to patients with multimorbidity in practices where the rate of patients with multimorbidity is high seems to increase risk of burnout among general practitioners (GPs) [11].

However, while the challenges are widely acknowledged [12] and there is some consensus about key components to improve care [13], knowledge of the most appropriate organisation of healthcare services to ensure patient-centred, high-quality integrated care for patients living with complicated multimorbidity is limited [14], [15].

In Denmark, general practice is the key organisational setting in terms of offering people with complicated multimorbidity integrated, patient-centred care. General practice has responsibility for the continued and longitudinal care of all patients' diseases. The approach is patient-centred and often includes collaboration with the families. A recent study showed that GPs provide chronic care to patients with multimorbidity, and those with low socioeconomic status, but service provision varied highly and more than expected across practices. Remarkably, GPs provided slightly fewer chronic care services than expected in practices where many patients with multimorbidity and low socioeconomic status were clustered, suggesting inverse care law mechanisms [16].

To improve care for patients with complicated multimorbidity in general practice, we developed a complex intervention model named, “patient-centred complex intervention in complicated multimorbidity (CIM)” [17]. The model was developed based on evidence from the Chronic Care Model [18], [19], models of care for multimorbidity [14], [15], [20], and results from our own research [3], [4]. Components of the CIM model included training of health professionals, a longer consultation time to facilitate patient-centred care [18], [19], [21] through the “overview consultation”, and reduction of control visits if appropriate. Further, integrated care was supported by a care coordinator, and shared patient information (individualized care plan) between organisations. The CIM model was tested in a feasibility study showing promising results regarding the implementation and acceptance of the CIM both by patients and healthcare professionals [17]. Based on the results from the feasibility study, and other national studies, the present project has developed an improved version of the CIM model named

the CIM2 model [17], [22]. The new CIM2 model includes improved training of healthcare professionals, strengthened identification of patients with complicated multimorbidity, adjustment of extended consultation according to the consultation model of DSAM, improved medical treatment, and strengthened integration of care services between healthcare organisations [17] [23].

The results from the first study of the CIM model [17] attracted the attention of policymakers in primary care, and the new collective agreement for general practice includes a plan to perform a large intervention project based on similar ideas and involving 600 GPs (hence labeled MM600 in the following). This has created a new critical potential for scaling up the elements from the CIM2 model at the national level. However, prior to large-scale implementation – and in accordance with the Medical Research Councils guidance on complex interventions [24] – the intervention must be pilot tested at a smaller scale in order to assess its functionality and effectiveness. For this purpose, we have designed the present pilot study named MM14 (since it includes 14 GPs). The MM14 pilot study will develop and strengthen the CIM2 model, and the results will be used to shape the MM600 national project.

### **Aim of the pilot study**

The overall aim of this study is to evaluate important aspects of the “Complex intervention for patients with complicated multimorbidity model, version 2” (CIM2 model) in a pilot cluster-randomised controlled trial (RCT) before conducting a larger cluster RCT[25] being part of the research project described in the Agreement between PLO and Danish Regions 2022 (OK22).

The evaluation of the pilot study has three main objectives [26]:

- 1) To assess the acceptability, workability and value of the model as experienced by health professionals and patients. In particular, this includes:
  - a) Assessing if and how the model supports patient-centred care as experienced by patients and professionals
  - b) Assessing if and how the model supports integrated care between general practice, hospital, and municipality as experienced by patients and professionals
  - c) Identifying important facilitators and barriers for implementing the model in practice.
- 2) To assess the acceptability and feasibility of the cluster RCT study design and procedures;
- 3) To assess and qualify the preliminary power calculations of the Patient Assessment of Chronic Illness Care (PACIC) questionnaire statistical estimates for the main RCT cluster study that is planned in the MM600 project.

The results from the pilot study will be used to develop and strengthen the CIM2 model and the design of the MM600 project.

### **Timeline**

[figure not shown]
The feasibility study took place in the years 2017-18 [17]. The pilot study (MM14), takes place in 2022-2023 with a three months inclusion period and 12-month intervention period. The main RCT study (MM600) will take place in 2023-2024.

### **Methods and design**

## Study principles and study design

The pilot study includes 14 general practice clinics – seven will be allocated to CIM2-group and seven will be allocated to perform usual care. Each practice will include 25 patients with complicated multimorbidity, thus, in total 350 patients. At 6 and 12 month intervention period, the patients' assessment of perceived patient-centred integrated care, health-related quality of life, and treatment burden will be measured in both groups (Figure 1).

Figure 1. The flow diagram illustrates the structure of the RCT pilot “A new care model for patients with complicated multimorbidity – A cluster-randomised pilot study in general practice, municipalities, and hospitals”. Patient Assessment of Chronic Illness Care (PACIC), EuroQol-5 Domain (EQ-5D-5L), Multimorbidity Treatment Burden Questionnaire (MTBQ).

## *Setting*

The study will be carried out in Region Zealand and the Capital Region of Denmark, in general practices in three municipalities, in close collaboration with healthcare centers in the municipalities and hospital medical departments hospitals. The general practices should have a minimum of 4,500 patients registered to make sure that the number of patients with complicated multimorbidity reaches the needed number of 25 patients per practice. In addition, the practice needs to be able to include a care coordinator a few hours per week for five months. The municipalities were selected based on the rank of sociodemographic groups (III and IV, lowest) as the prevalence of patients with complicated multimorbidity is higher and the patients are sicker from their multimorbidity. Moreover, the possible benefits of the CIM2 model are expected to be larger in patients from municipalities of these sociodemographic groups.

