### Eligible patients

The healthcare professionals in general practice identify eligible patients for the project. Identified patients receive oral and written information about the study from the care coordinator. Patients who agree to participate provide informed consent for participation in the study collected by the care coordinator.

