### The intervention elements in the CIM2 model (Figure 2.)

- Training of healthcare professionals during a four-hour one-day course

The training program is developed in collaboration with The Danish College of General Practitioners. Healthcare professionals from general practice, nurses and physiotherapists from the municipalities, and healthcare professionals from the out-patient clinics participate in a training program. Healthcare professionals from general practice will receive training in project content, and methods to recruit and include patients (including informed consent). Further, does the education program offer training in the collection of patient data comprising the use of REDCap software for patient questionnaires.

[figure not shown]
For general practices allocated to the intervention group, the training also includes how to provide medical care for patients with complicated multimorbidity, case-based teaching, patient centred methods, structure and implementation of the extended overview consultation, and development of the care plan. Further, the training cover methods for improving collaboration and integration between general practice, the municipality, and the out-patient clinics using methods known from the national disease management programs.

- The extended overview consultation (in Danish “overblikskonsultation”) in general practice

The patient intervention starts with an extended overview consultation, lasting 45 minutes, with the GP, the patient (and maybe a relative), and the care coordinator. The consultation is based on the guidance for a patient-centred overview status for patients with multimorbidity published by The Danish College of General Practitioners [29]. The aim is to get an overview of the patient’s conditions, problems, and needs. The patient’s goals, preferences, and needs are identified, and treatments of the patient’s various conditions are prioritized. The GP decides who has the treatment responsibility for each condition. The patient’s resources for handling the chronic diseases are elicited, and if the patient is motivated, a referral to a relevant rehabilitation program in the municipality is planned [30]. The individual care plan is developed, covering planned activities in the three sectors that will take place within the 12-month intervention period. The GP will try to reduce the number of outpatient visits in the hospital or replace

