outpatient visits with GP visits if the patient and the specialist agree. The GPs are reimbursed with 1.000 DKK. for the extended overview consultations

Figure 2. Central activities during the implementation and intervention phases of the study “Complex intervention for patients with complicated multimorbidity model version 2 (CIM2)” over time.

- The individual care plan

The individual care plan includes 6 themes: [29] 1) Listing of important diagnoses, 2) Overview of the patient's prescription drugs, 3) Prioritising the patients' treatment goals (using shared decision-making), 4) Development of a coordinated care plan with telephone follow-up and future visits, 5) Plan for potentially reducing the number of visits to hospital out-patient clinic for example by shifting hospital out-patient clinic visits to general practice, and 6) Referral to community-based rehabilitation. The care plan is printed for the patient.

- Care coordinator

General practice coordinates the planned patient care between general practice, the municipality, and the hospital, and follow-up on the execution of planned healthcare activities. The care coordinator function might be undertaken by the GP or the nurse in the practice. The practice plans the division of responsibilities and tasks in the project between the GP and the nurse.

- Follow-up activities

The follow-up activities include telephone calls to the patient by the care coordinator at relevant time intervals according to the severity of conditions and other important factors to follow up on planned activities with the patient. A second extended overview consultation takes place after 12 months.

- Integration of care elements

The individual care plan is shared electronically with the healthcare center in the municipality and with the outpatient clinics using the standard IT-communication tool provided by MedCom and a routinely used national standard in general practice, hospitals, and municipalities.

The GPs and hospitals are offered the opportunity for using cross-sectorial video conferences to plan the patient pathway as described in the OK22. This means that the GP arranges the conference when there is a professional indication for the conference. The GPs' participation in the videoconference is reimbursed.

The health professionals in the municipality provide information to the GP when patients have finished a rehabilitation program.

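### Does requiring a care coordinator for five months conflict with an intervention that runs for 12 months?

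*Protocol*

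**What the plan says.** The five months appears once, in the protocol's Setting section, next to the minimum list size. Both are conditions a practice must meet to take part: "the practice needs to be able to include a care coordinator a few hours per week for five months". No start point, end point or list of tasks is attached to it.

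The coordinator's work is described elsewhere in the protocol:

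- **Timeline:** the pilot runs "with a three months inclusion period and 12-month intervention period".
- **Eligible patients:** the coordinator informs patients, and "Patients who agree to participate provide informed consent for participation in the study collected by the care coordinator".
- **The intervention elements in the CIM2 model, overview consultation:** the coordinator takes part in the opening consultation, which produces a care plan "covering planned activities in the three sectors that will take place within the 12-month intervention period".
- **Same section, care coordinator:** "The care coordinator function might be undertaken by the GP or the nurse in the practice". The practice decides how the tasks are divided.
- **Same section, follow-up activities:** "The follow-up activities include telephone calls to the patient by the care coordinator at relevant time intervals", adapted to the severity of the patient's conditions, and "A second extended overview consultation takes place after 12 months".

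The first objective in the Aim of the pilot study is "To assess the acceptability, workability and value of the model as experienced by health professionals and patients".

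**The concern.** Set beside the Timeline, the figure looks too small. Consent work falls within the three months of inclusion, and follow-up of the care plan belongs to the 12 months after that. Five months cannot span both, wherever it starts.

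Two things could be at stake:

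- If coordination continues past five months, practices may have agreed to more work than the entry requirement suggests. That would matter in a pilot that is meant to judge workability and to inform the larger MM600 trial.
- If coordination stops at five months, the 12-month PACIC would be measured after one component of the model had ended. Depending on the start date, so would some or all of the 6-month measurements.

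The visible text does not say outright which of these was intended.

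**Working it through.** The five months is stated without a derivation, so there is no figure of the plan to reproduce. The check compares periods by addition and then asks what the text supports.

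**Inputs.** Required coordinator availability, 5 months (Setting). Inclusion, 3 months, and intervention, 12 months (Timeline). Questionnaires at baseline, 6 and 12 months (Evaluation and data collection). Assumption: each patient's 12 months start at enrolment, at calendar month e, with e between 0 and 3.

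**Task span per practice.** 3 + 12 = 15 months. Five months is 5/15 = 33% of this, and 5/12 = 42% of one patient's intervention.

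**If the five months start when inclusion opens.** They end at follow-up month 5 − e, which is month 5 for the first patient and month 2 for the last. The gap to month 12 is 12 − 5 = 7 to 12 − 2 = 10 months.

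**If they start when inclusion closes.** They end at follow-up month 3 + 5 − e = 8 − e, which is month 8 for the first patient and month 5 for the last. The gap to month 12 is 12 − 8 = 4 to 12 − 5 = 7 months. The information and consent work then lies outside the five months.

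So no start date lets five months cover every task. These figures would bear on the PACIC only if coordination ended when the five months did. Four features of the text show that this premise is unsupported:

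1. *The kind of statement.* The Setting section says what a practice must be able to offer in order to be eligible. It does not describe how long patients are coordinated. The sections that do describe coordination give no five-month limit, and the care plan they refer to covers 12 months.
2. *Who does the work.* The role may be filled by the GP or nurse already in the practice. Calls come at intervals suited to the patient, with no weekly quota. A weekly allowance for the concentrated early work (recruiting 25 patients and holding the first consultations), followed by occasional calls by existing staff, fits everything written.
3. *Who the requirement applies to.* It applies to all 14 practices before allocation. Under usual care, the visible text gives the coordinator only information and consent work. The overview consultations and follow-up calls belong to the intervention arm. A requirement common to both arms need not equal the workload of one, so 33% compares unlike things.
4. *What cannot be seen.* The timeline figure and Figure 2, whose caption says it shows central activities over time, are not reproduced in the text at hand. Practices that agree to take part also receive detailed study information (Randomization and blinding), which is not shown.

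**Effect on the statistics.** The power calculation uses a difference of 0.36, a total variance of 1, an ICC of 0.1, 25 patients per clinic, 30% loss to follow-up and 7 clinics per arm, and reports 84% power. None of these inputs depends on the coordinator's hours.

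**The case for a change.** The strongest case for acting is that staff time is central to workability, that practices accept the requirement before they know their arm, and that one sentence would remove the doubt. Even a figure that placed the five months in time could not make it span all the tasks in the text. Someone has to supply the later hours.

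Part of this stands. The arithmetic is right, and the visible text leaves the start, scope and arm coverage of the five months unstated. That the period means start-up time is itself an inference.

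The consequences do not stand. An understated workload has not been shown, because the fuller information given to practices is not available and the function may pass to existing staff. If later coordination does prove burdensome, the pilot is built to find out: GPs and practice nurses in the seven intervention practices are interviewed at the end about how the model works in practice, with delivery data from REDCap alongside. Nor is a new data field for dated coordinator contacts shown to be needed, because the protocol lists its delivery data only as examples, so the absence of coordinator contacts does not show that they go unrecorded.

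**Conclusion.** The concern does not call for a change. The five months is shorter than the span of the coordinator's tasks (5 against up to 15 months per practice), but it is an entry criterion for practices and does not limit the coordination patients receive. There is no strict contradiction. Stating what the period covers would help a reader, but it would alter no estimate, test or conclusion if the plan is followed as written.

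This rests on reading the requirement as capacity, and on the absence of any text that ends coordination at five months. The calculated gaps of 4 to 10 months before the 12-month questionnaire describe only the case in which coordination does stop, with enrolment spread over three months, and the protocol gives no support for that case. No view is taken here on how long coordination should last.

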### *Randomization and blinding*

General practices in the designated municipalities are contacted with an invitation to participate in the study. If a general practice agrees to participate in the project, they will receive detailed study information. The 14 participating general practices will be randomised into either the intervention group providing care as described in the CIM2 model or the control group, providing usual care. The general practices will be randomly allocated, at an allocation rate of 1:1, by a computer program. To ensure concealment of allocation, a data manager from another organisation with no interest in the project will provide the information of the randomization to the general practice draw and will be responsible for a randomization list, which will be available to the investigator. Due to the nature of the study, the general practices and the patients cannot be blinded.

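### The allocation rule for 14 practices in three municipalities names no restriction on municipality, so chance imbalance is likely and costs precision that a constrained draw would largely save

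*Protocol*

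**What the plan says.** Under Study principles and study design, 14 practices are divided equally: "seven will be allocated to CIM2-group and seven will be allocated to perform usual care". Under Randomization and blinding, the rule is: "The general practices will be randomly allocated, at an allocation rate of 1:1, by a computer program". That section adds who holds the list and who cannot be blinded. It mentions no stratification, matching, minimisation or other constraint.

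Under Setting, the trial runs "in general practices in three municipalities, in close collaboration with healthcare centers in the municipalities". The municipalities lie in two regions and were chosen on a known characteristic: "The municipalities were selected based on the rank of sociodemographic groups (III and IV, lowest". The same paragraph links that rank to how common complicated multimorbidity is, how ill the patients are, and how much benefit is expected from the model.

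The section on the intervention elements makes municipal services part of what is tested:
- Training: "nurses and physiotherapists from the municipalities, and healthcare professionals from the out-patient clinics participate in a training program".
- Care plan: "The individual care plan is shared electronically with the healthcare center in the municipality and with the outpatient clinics".
- Rehabilitation: if the patient is motivated, "a referral to a relevant rehabilitation program in the municipality is planned".

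The power model, under the third evaluation objective, has a group effect and a clinic random effect. It has no municipality term.

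**The concern.** Municipality is known before any practice is allocated. By the protocol's own account it delivers part of the integrated care that patients are asked to rate, and the sociodemographic rank on which it was chosen is tied to severity and expected benefit. With only 14 clusters, a draw that ignores it will often leave the arms uneven across municipalities.

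At stake is the precision of the PACIC comparison. If the analysis does not adjust, differences between municipalities enter the arm difference as extra error. If it does adjust, an uneven draw leaves less within-municipality information to estimate the effect from. Adjustment can be decided later, but balance can only be secured before the draw. The restriction therefore belongs in the randomisation section and cannot be left to an analysis plan.

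**Working it through.** **Inputs from the protocol.** 14 practices, 7:7, three municipalities; PACIC difference 0.36; ICC 0.1; total variance 1; 25 patients per clinic with 30% loss, so 25 × 0.7 = 17.5 completers; two-sided 5% test.

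**Assumed, because the protocol does not give them.** Practices per municipality (five splits from 5/5/4 to 8/3/3), and the share *s* of between-clinic variance explained by municipality (25% or 50%).

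**The plan's own figure.** The protocol states 84% power for 7 clinics per arm. From its inputs, SE = √[2 × (0.1 + 0.9/17.5)/7] = √[2 × 0.1514/7] = 0.208. Power at 0.36 is 41% by normal approximation and 35.7% by noncentral t with 12 degrees of freedom. The 84% does not reproduce. That is a separate matter and adds no weight here; the t-based 35.7% serves only as the baseline.

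**Step 1: how often the draw is uneven.** There are C(14,7) = 3432 equal allocations. For municipality sizes n₁, n₂, n₃, the number placing a₁, a₂, a₃ practices in the CIM2 arm is C(n₁,a₁) × C(n₂,a₂) × C(n₃,a₃), with a₁ + a₂ + a₃ = 7.

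Example, 5/5/4. Draws with every gap at most one: 2 × C(5,2) × C(5,3) × C(4,2) = 2 × 10 × 10 × 6 = 1200. So P(some gap of two or more) = 1 − 1200/3432 = 65.0%.

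Example, 8/3/3. Each small municipality lies wholly in one arm in C(11,7) + C(11,4) = 660 draws. Both do so in 8 + 8 + 70 + 70 = 156. The large one cannot. So (660 + 660 − 156)/3432 = 1164/3432 = 33.9%.

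| Assumed split | Draws with all gaps ≤ 1 | Some gap ≥ 2 | Some municipality wholly in one arm |
|---|---|---|---|
| 5/5/4 | 1200 | 65.0% | 9.7% |
| 6/4/4 | 720 | 79.0% | 12.8% |
| 6/5/3 | 1200 | 65.0% | 20.5% |
| 7/4/3 | 1260 | 63.3% | 24.1% |
| 8/3/3 | 1260 | 63.3% | 33.9% |

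All three municipalities separate completely by arm in no draw for four of the splits, and in 2/3432 = 0.06% for 7/4/3. A balanced draw exists for all five.

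**Step 2: size of the chance shift without adjustment.** If municipality effects have variance τ², the arm difference shifts with SD √{τ² × mean of Σ[(2aⱼ − nⱼ)/7]²}. For τ² = 0.02 to 0.05 (20-50% of the between-clinic variance of 0.1, assumed), this is about 0.06 to 0.10 for an unconstrained draw and 0.00 to 0.045 for a constrained one, against a target of 0.36.

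**Step 3: precision with municipality adjusted for in both cases.** The clinic-mean variance is v = 0.1(1 − s) + 0.9/17.5, and SE = √(v/I), where I = Σ aⱼ(nⱼ − aⱼ)/nⱼ.
- Unconstrained: the mean of aⱼ(nⱼ − aⱼ)/nⱼ is (nⱼ − 1) × 7/26, so the mean of I is (14 − 3) × 7/26 = 2.96 for every split.
- Constrained: I is 3.5 for 6/4/4 (1.5 + 1 + 1) and 3.33 for 8/3/3 (2 + 0.67 + 0.67), with the other splits in between.

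Power is by noncentral t with 12 − 2 = 10 degrees of freedom, averaged over all draws in the unconstrained case:

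| Share s (assumed) | v | Unconstrained, adjusted | Constrained, adjusted | Constrained SE |
|---|---|---|---|---|
| 25% | 0.1264 | 35% | 39-40% | 0.190-0.195 |
| 50% | 0.1014 | 42% | 46-48% | 0.170-0.174 |

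**Step 4: cost if municipality is uninformative (s = 0).** v = 0.1514, so the SE is 0.208 (6/4/4) to 0.213 (8/3/3). With 10 degrees of freedom, power is 34.7% to 33.3%, against 35.7% unadjusted: a loss of 1.0 to 2.4 points.

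**The case against.** The strongest reply is that this is a pilot. Its stated aims are acceptability, feasibility and checking the power assumptions for the main trial; a powered PACIC contrast is not among them, and on these figures the contrast stays below 50% power either way. PACIC is also measured at baseline, so existing municipal differences in perceived care can be seen and adjusted for. Register data are to be used to compare the arms. Choosing municipalities only from groups III and IV narrows the differences between them. All of this stands and keeps the consequence moderate. It does not remove the point: these measures act after allocation, and the pilot is also meant to test the randomisation procedure that the main trial would use.

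Stronger readings are tempting but not supported:
- A reader might infer that municipality is confounded with arm. Complete separation is practically impossible (at most 0.06% of draws). If one municipality falls in one arm, the others still supply within-municipality contrasts. The problem is chance imbalance.
- A reader might take the protocol to say that allocation is unrestricted. It fixes the 7:7 total and is silent on anything further, so the absence of a municipality constraint is inferred from that silence.
- A reader might suppose that each municipality has its own hospital partners. The Setting section does not say how hospitals map to municipalities; the argument rests on municipal services alone.
- A reader might credit the constraint with the whole rise from 36% (unconstrained, unadjusted) to as much as 48% (constrained, adjusted). Part of that rise comes from adjustment. Like for like, the constraint adds about 4 to 6 points.

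**Conclusion.** The point holds as a cheap design improvement, not as an error or a source of systematic bias. Under the assumed splits, an arm gap of two or more practices in some municipality is more likely than not (63-79%), and a municipality wholly in one arm is a realistic possibility (10-34%). Constraining the draw is worth about 4 to 6 points of power on the PACIC contrast if municipality explains 25-50% of between-clinic variance.

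The imbalance figures depend on how many practices each municipality contributes, and the power figures also depend on that variance share. The protocol gives neither. If the share is zero, the change loses a little power. If the allocation program already restricts on municipality, one sentence saying so settles the matter.

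**What to change.** In Randomization and blinding, state that all 14 practices are allocated in one step by randomisation constrained on municipality: seven per arm, with arm counts within each municipality differing by at most one. The 7:7 total allows this for all five splits examined, and between 720 and 1260 allocations remain to draw from. Account for municipality in the PACIC analysis; that part may sit in the statistical analysis plan.

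The cost is a few lines in the allocation program, and all 14 practices must have agreed before the draw. No extra practices, patients or visits are needed. As a fixed effect, municipality takes two degrees of freedom, or about 1.0-2.4 points of power against an unadjusted analysis if it turns out uninformative.

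The constraint does not prevent contamination: the same municipal staff may serve patients of both arms, and balancing the arms within municipalities does not change that.
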